#### 3.7. CLINICAL UTILITY/NET BENEFIT

Decision curve analysis will be used to assess and compare the utility of the models (both regression model and machine learning approaches) and to explore at 25% of threshold which calculates the net benefit of using the model (compared to not using the model). The net benefit of a model is the difference between the proportion of true positives and the proportion of false positives weighted by the odds of the selected threshold for high-risk designation [36].

#### 3.8. EXTERNAL VALIDATION

### 3.8.1. STUDY SETTING AND DATA COLLECTION (VALIDATION DATASETS)

The developed models will be validated on three datasets. These are:

**Brigham and Women's Hospital**: The Brigham and Women's CABG Genomics Database is a prospective single centre and detailed research database comprising over 2000 surgeries from 2001-2016. This dataset contains over 1,700 prospectively collected and curated pre, intra, and post-operative variables.

**NHS Trusts:** The study will prospectively collect data from the UK NHS Trusts which will allow us to undertake external validation of PARADISE-1/PARADISE-2 with a total of approximately 6000 patients (2000 AFACS events) per annum. The NHS Trusts where data will be extracted from are:

- Liverpool Heart & Chest NHS Foundation Trust
- Barts Heart Centre (Barts Health NHS Trust)
- Oxford University Hospitals NHS Foundation Trust

Tight K study (trial dataset): (BHF-funded CS/18/3/34063, ClinicalTrials.gov Identifier: NCT04053816). Tight K is a 22-centre clinical trial that will include 1684 patients, randomised within this non-inferiority trial to investigate whether maintaining serum potassium ≥3.6mEq/L is equivalent to maintaining levels at 4.5- 5.5mEq/L, with a primary endpoint of development of AFACS using precise clinical definitions and 5-day Holter monitoring. The trial is already designed to collect detailed data on AFACS risk factors, minimising any additional burden of PARADISE. It is restricted to patients undergoing isolated coronary artery bypass grafting. This has the strength that detailed data are being collected in a well-defined cohort, but means we need additional prospective data to assess the performance of the PARADISE scores in valve surgery.

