5.2 Aim

The study aims to develop and validate two clinical prediction models to estimate the risk of a patient developing AF in the seven days following cardiac surgery, using data available:

- In the pre-operative assessment clinic or on admission for surgery (PARADISE-1)
- On arrival in the post-operative care unit (PARADISE-2)

Objectives	Outcome Measures	Timepoint(s) of evaluation of this outcome measure (if applicable)
Primary Objective To develop and externally validate two prognostic models to predict post-operative atrial fibrillation after cardiac surgery using data available in the pre-operative assessment clinic or on admission for surgery (PARADISE-1) and on arrival in the post-operative care unit (PARADISE-2); and compare their performance to other published models	 Primary outcome Discrimination (c-statistic) and calibration (intercept and slope) in external dataset Secondary outcomes Positive and negative predictive values, sensitivity and specificity 	7 days after cardiac surgery

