7.2.2 Trial data sets

Clinical Research Protocol Template version 15.0

CONFIDENTIAL

© Copyright: The University of Oxford and Oxford University Hospitals NHS Foundation Trust 2019 Page 14 of 34 1. Tight K study: (BHF-funded CS/18/3/34063, ClinicalTrials.gov Identifier: NCT04053816). Tight K is a 22-centre clinical trial that will include 1684 patients, randomised within this non-inferiority trial to investigate whether maintaining serum potassium ≥3.6mEq/L is equivalent to maintaining levels at 4.5- 5.5mEq/L, with a primary endpoint of development of AFACS using precise clinical definitions and 5-day Holter monitoring. The trial is already designed to collect detailed data on AFACS risk factors, minimising any additional burden of PARADISE. It is restricted to patients undergoing isolated coronary artery bypass grafting. This has the strength that detailed data are being collected in a well-defined cohort, but means we need additional prospective data to assess the performance of the PARADISE scores in valve surgery.

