12.3 Data Recording and Record Keeping

All study records will be electronic – an overview of their generation is detailed above. All records will be subject to quality assurance polices both at the University and research group level. These are designed to guarantee the accuracy and validity of the study data.

The participants will be identified by a unique study number (pseudonymous study key).

We will use the CALIBER and PRD data sources to validate known (and potentially identify novel) risk factors for AF after cardiac surgery. A complete list of risk factors will not be known a priori, as it depends on the results of the systematic review and Delphi process. However, likely required data will be contained within following categories:

- Demographics (e.g., age, sex, ethnicity)
- Diagnostic coding (e.g., known chronic conditions)
- Limited pre- and post-operative medications (e.g., beta-blockers, vasoactive drugs)
- Limited surgical procedures and intraoperative findings (e.g., type of cardiac surgery, duration of bypass, blood transfusion)
- laboratory blood tests (including blood gases)
- vital signs (e.g., heart rate, blood pressure)
- Limited Echocardiogram findings
- Limited electrocardiogram (ECG) findings

Excluding age, sex and ethnicity we will not be accessing data on protected characteristics (e.g., religion, civil status, sexual orientation).

The expert panel will agree a final list of risk factors, which will be used to develop the two prediction models.

The models will be validated in one US data set (Brigham), one clinical trial data set (Tight-K) and prospective data collected from UK cardiac surgery centres (NHS Trusts). Only data from the above categories included in the candidate risk factor list agreed by the expert panel will be extracted from the UK cardiac centres along with the required outcome data for model assessment (including in-hospital

CONFIDENTIAL

mortality and episodes of atrial fibrillation). Tight-K is an ongoing clinical trial with its own approvals. Data for the NHS Trust data sets will be acquired from the individual Trusts patient records in collaboration with the respective organisations.

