#### 3.2. OUTCOME MEASURE

A new onset atrial fibrillation was defined as present if current atrial fibrillation or flutter was mentioned in patient cardiac report (e.g., ECG, ECHO) OR atrial fibrillation was identified by a trained chart abstractor for The Society of Thoracic Surgeons Adult Cardiac Surgery Database during postoperative period during the hospital admission (the outcome was assumed to happen within 7 days when timing was not specified).

Prior AF status was defined as any previous history of AF. Models for prior AF patients will be investigated in the sub analysis (section 3.6)

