#### 3.3.1. Study setting and data collection

We will use the Massachusetts General Hospital (MGH) database to develop the PARADISE prediction models. The MGH dataset has two data sources:

- 1. the Research Patient Data Registry (RPDR): medical record data extracted from electronic hospital systems
- 2. the Society of Thoracic Surgeons (STS) Adult Cardiac Surgery Database: data gathered by trained extractors

Both data sources for the Mass General Hospital dataset will be used to develop our models and we will use retrospective pre-, intra-, and post-operative data for over 10,000 cardiac surgeries performed and recorded at this single US centre between 2003 and 2020.

It is important to note that some tables from this dataset were affected by a change in its electronic medical record system, which changed from Longitudinal Medical Record (LMR) to EPIC in April 2016.

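### Does the SAP need a rule for mapping Tight-K's 5-day Holter endpoint to the 7-day AF outcome?

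*SAP*

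**What the plan says.** The objectives table in the protocol (section 5.2) makes "Discrimination (c-statistic) and calibration (intercept and slope) in external dataset" the primary outcome, evaluated at "7 days after cardiac surgery". SAP 2.1 and SAP 3 state the same seven-day target for the whole study.

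SAP 3.2 holds the only outcome definition. AF is present if "current atrial fibrillation or flutter was mentioned in patient cardiac report (e.g., ECG, ECHO", or if a trained abstractor for the US cardiac surgery registry found it during the admission. It adds that "the outcome was assumed to happen within 7 days when timing was not specified". SAP 3.3.1 lists that registry as one of the two sources of the Massachusetts General (MGH) development data. For the NHS Trusts, protocol 12.3 lists "mortality and episodes of atrial fibrillation" among the outcome data to be extracted.

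For Tight-K, SAP 3.8.1, like protocol 7.2.2, describes a trial "with a primary endpoint of development of AFACS using precise clinical definitions and 5-day Holter monitoring", and notes that the trial is limited to isolated bypass grafting. SAP 3.8.2 then compares model predictions with observed outcomes in each of the three data sets. It gives no data-set-specific outcome rule.

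**The concern.** A model built for a seven-day outcome seems about to be checked against a five-day one in Tight-K, with a different way of finding AF. Two effects would then enter the Tight-K intercept alongside any real miscalibration. A shorter window loses AF that starts on days 6 and 7. Continuous monitoring picks up AF that routine records may miss. They act in opposite directions, so an intercept near zero would not by itself show good calibration for the seven-day outcome, and one away from zero would not by itself show poor calibration.

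The intercept is part of the primary outcome. The recalibration step in SAP 3.8.2 is motivated by case-mix, including outcome prevalence, so a measurement difference could be read as a case-mix difference. That section also does not say which of the two UK data sets decides whether to recalibrate.

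**Working it through.** **The plan's own figure.** The nearest stated number is the observed/expected (O/E) sample size in SAP 3.8.2: n = (1 - p)/(p × SE²). With p = 0.20 and SE = 0.2/3.92 = 0.051, n = 0.80/(0.20 × 0.051²) = 1538, which matches the SAP. O/E appears in the plan only as this sample-size criterion. The planned calibration measures are the plot, slope and intercept (SAP 3.5.1).

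**Inputs for the window effect.**
- AF timing (SAP 2): 70% before day 4, 94% by day 7. Read plainly, this is 70% by the end of day 3.
- Prevalence 20% and c-statistic about 0.72 (SAP 3.8.2).
- Tight-K size 1684 (SAP 3.8.1). Protocol 7.5 expects one half to two thirds of trial recruitment to be available. Applied to 1684 (an assumption, since that sentence also covers a second trial), this gives 842 to 1123.

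**Share f of seven-day AF seen by day 5.**
- Linear: 24 points over 4 days is 6 a day, so 70 + 12 = 82% by day 5, and f = 0.82/0.94 = 0.872.
- Constant hazard: ln(0.30/0.06)/4 = 0.402 a day; cumulative share by day 5 = 1 - 0.30 × exp(-0.804) = 0.866, and f = 0.866/0.94 = 0.921.

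**Intercept shift for a model perfectly calibrated to seven days.** Take a normal linear predictor with mean -1.592 and SD 0.872, which gives 20% prevalence and c = 0.72. Solve for the shift a at which the mean of expit(a + LP) equals 0.20 × f.
- f = 0.921: a = -0.114
- f = 0.872: a = -0.187

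**Sampling error of the intercept.** The 95% half-width is 1.96/√(N × I), where I is the mean of p(1 - p) under the same model.
- N = 1684: 0.126
- N = 1123: 0.155
- N = 842: 0.179

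The window effect is therefore comparable with sampling error. At full size it runs from just inside the half-width to about one and a half times it (0.187/0.126 = 1.5). At N = 842 it runs from well inside to about equal. The shifts in slope (0.97 to 0.95) and c-statistic (0.716 to 0.713) are small beside their half-widths at N = 1684, about 0.16 and 0.03.

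**Detection.** The documents give no figure. A relative gain of 1/0.921 = 1.09 to 1/0.872 = 1.15 would cancel the window effect, and a larger gain would reverse its sign.

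**No firm lower limit.** One might take 0.70/0.94 = 0.745 as the smallest possible f. It is not a floor here. SAP 3.2 counts untimed in-hospital AF as seven-day AF, so the development outcome may itself include later AF. If it included all of it, the share would be 0.70.

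**What the figures depend on.** Each needs the Tight-K endpoint to be the variable scored. Protocol 7.2.2 and SAP 3.8.1 give that endpoint while describing what the trial is. Neither says PARADISE will use it, and neither says whether Tight-K records AF on days 6 and 7 or off the monitor.

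**The case for a change.** The strongest case for acting is that the gap is real. No section says which Tight-K AF variable counts, over which days or from which source, and without a rule the choice could be made after results are seen. Tight-K is one of only two UK validation sets. Naming the variable would cost a sentence.

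The gap itself stands. It is an unfilled detail, however, not an instruction that would mislead. Followed as written, the plan scores seven-day AF, and the first limb of SAP 3.2 can be applied to any source of cardiac reports. Tight-K results will stand beside the larger NHS cohort, and protocol 7.5 already says that trial and routine data have different strengths and weaknesses.

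The more ambitious remedies do not clearly improve matters. Putting routinely recorded AF ahead of Holter data reverses a preference the protocol has grounds for, since it counts the trial's definitions and data quality as strengths. A matched five-day analysis in NHS data would deal with the window but not with detection, the part nobody can size from the documents. It would also need NHS isolated-bypass patients with dated onset, whose number is not given.

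Which UK data set decides on recalibration is a separate open detail. Tight-K's restriction to isolated bypass grafting would raise it without any Holter difference.

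**Conclusion.** No change to the plan is needed. The SAP leaves the Tight-K outcome variable unnamed, and a sensible analyst fills that gap by choosing the variable closest to seven-day AF and stating its limits beside the Tight-K results.

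If the five-day endpoint were used, the window alone would shift the intercept by about -0.11 to -0.19, against a half-width of 0.13 to 0.18. This assumes 20% prevalence, a c-statistic of 0.72, 70% of AF by the end of day 3 and no difference in detection. With a detection gain the net direction is unknown, so the figures illustrate a possible distortion and do not show a bias in the plan. The conclusion rests on reading the seven-day target and SAP 3.2 as applying to the whole study, which their place in the SAP supports.

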2 LAY SUMMARY

Atrial Fibrillation (AF) is a common abnormal heart rhythm. AF causes the heart to beat irregularly and sometimes very rapidly. About 30-50% of patients develop AF after heart surgery. These patients stay longer on the Intensive Care Unit (ICU) after surgery, are more likely to develop complications and have a higher risk of dying. Avoiding AF is important.

Some drugs, including beta blockers and amiodarone may help prevent AF if given after surgery. However, these may also lead to complications (such as lung damage). It is therefore important to identify which patients are most likely to benefit from these treatments (i.e., where the benefits outweigh the risks). There are existing tools designed to predict the risk of suffering AF after heart surgery. However, they are unreliable and therefore not used in clinical practice. A modern, reliable risk prediction tool is needed.

The PARADISE study will develop and test new prediction tools to identify which patients are most at risk of developing AF after heart surgery. We will focus our tools on those patients who most commonly develop AF, such as those who have had surgery to repair a valve or blood vessel in their heart.

To do this we will:

- Review the medical literature and assemble a panel of medical experts to create a list of known factors that affect patients' risk of AF after heart surgery
- Use a large UK general practice database (CALIBER) to see whether we can find new risk factors.
- Ask the expert panel to agree a list of known and new risks factors to be included in the prediction tool.
- Develop two new prediction tools using an existing American cardiac surgery database (the Partners research Database). The first will be used before surgery, the second immediately following surgery. Two models are needed as events during surgery may alter the risk of AF.
- Test how reliably our new tools predict which patients suffer AF after surgery, with data from large UK NHS heart centres, one US Hospital (Brigham) and a UK clinical trial (Tight-K).
- We will work with two charities (AF Alliance and StopAfib) to share our results with patients and the wider public.

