3 SYNOPSIS

Study Title	Predicting AF after Cardiac Surgery - the PARADISE Score. A Clinical Prediction Rule for Post-operative Atrial Fibrillation in Patients Undergoing Cardiac Surgery			
Internal ref. no. / short title	PARADISE			
Study registration	ClinicalTrials.gov: NCT05255	5224		
Sponsor	University of Oxford Clinical Trials & Research Go [name], United Kingdom	overnance,		
Funder	NIHR National Institute of H Programme (NIHR131227)	ealth Research, Health Technol	ogy Assessment	
Study Design	Longitudinal cohort study			
Study Participants	Patients who have undergo	ne cardiac surgery		
Sample Size	Retrospective: 38, 000 Prospective: 13, 684			
Planned Study Period	Funded study period: 1 st Feb	oruary 2021 to 30 th June 2024		
	Prospective sub-study perio	d: 1 st October 2021 to 31 st July	2023	
Planned Recruitment period	Retrospective: 1 st January 19 Prospective: 1 st October 202			
	Objectives	, Outcome Measures	Timepoint(s)	
Primary	Primary Objective To develop and externally validate two prognostic models to predict post- operative atrial fibrillation after cardiac surgery using data available in the pre- operative assessment clinic or on admission for surgery (PARADISE-1) and on arrival in the post- operative care unit (PARADISE-2); and compare their performance to other published models	Primary outcome Discrimination (c-statistic) and calibration (intercept and slope) in external dataset Secondary outcomes Positive and negative predictive values, sensitivity and specificity	7 days after cardiac surgery	
Secondary	 Systematic literature review Analysis of CALIBER database using statistical and machine learning methods 	Candidate risk factors for inclusion in new onset atrial fibrillation prognostic models	For pre-operative model, factors up to surgery, for post-operative model factors up to 12 hours post surgery.	

Clinical Research Protocol Template version 15.0

CONFIDENTIAL

© Copyright: The University of Oxford and Oxford University Hospitals NHS Foundation Trust 2019 Page 8 of 34

development

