Both regression models and machine learning approaches will then be externally validated on prospective data from one US hospital (Brigham and Women's Hospital), prospectively collected data from UK NHS Trusts and one UK clinical trial (Tight K study). In brief, for each individual in these datasets, outcome predictions will be calculated using the model developed with the Massachusetts General Hospital dataset and compared with the observed outcomes. The performance of the prediction models will be characterised by evaluating calibration and discrimination. To account for potential differences in case-mix (distribution of patient characteristics and prevalence of the outcome) between the US data (Massachusetts General Hospital dataset) used to develop the model and the prospective external validation, we will investigate whether recalibration is needed to update the model to better fit the UK population [35].

Heterogeneity in model performance will be explored over different hospitals using internal-external cross-validation [40, 41].

Finally, we will compare our prediction models to those existing prediction models identified from the systematic review where sufficient details are available from the original publication and predictors are available in the US data set.

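### Prospective data beyond Tight K are said to be needed to judge the scores in valve surgery, but no analysis of performance by surgery type is planned

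*SAP*

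**What the plan says.** **The valve purpose.** On Tight K, Protocol 7.2.2 states: "It is restricted to patients undergoing isolated coronary artery bypass grafting". SAP 3.8.1 repeats this and adds that "we need additional prospective data to assess the performance of the PARADISE scores in valve surgery"; Protocol 7.2.2 carries the same conclusion. The protocol's lay summary describes the target patients as those who most often develop AF, "such as those who have had surgery to repair a valve or blood vessel in their heart". Both background sections say the risk is higher with isolated or combined mitral valve surgery.

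**The validation sets (SAP 3.8.1).**
- Tight K: isolated CABG only.
- Brigham: "CABG Genomics Database is a prospective single centre and detailed research database comprising over 2000 surgeries from 2001-2016". Its valve content is not stated.
- NHS Trusts: "approximately 6000 patients (2000 AFACS events) per annum". The valve share is not stated. Eligibility covers cardiac surgery generally, subject to the exclusions in SAP 3.1.2.

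**The planned analysis.** After describing individual predictions in each dataset, SAP 3.8.2 says: "The performance of the prediction models will be characterised by evaluating calibration and discrimination". It adds possible recalibration to the UK population, heterogeneity across hospitals and comparison with published models. SAP 3.6 plans one sub-analysis, on prior AF. Protocol 11.4 takes all eligible participants in each dataset. The validation sample size in SAP 3.8.2 has no valve component.

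**The concern.** The documents give assessment in valve surgery as a reason for prospective data beyond Tight K, but no planned step turns those data into that assessment. Someone following the plan exactly would obtain one NHS result mixing CABG, valve and other operations. Results by hospital or by prior AF would not separate valve from CABG.

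Because risk differs by procedure, the mixed result need not describe either group. Part of the pooled c-statistic may come from telling valve from CABG patients rather than from ranking patients within a procedure. Calibration errors of opposite sign in the two groups can also offset each other. If the scores are then offered for valve patients, that use would rest on figures that were never checked in them. Strata chosen after results are seen would carry less weight than pre-specified ones.

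**Working it through.** **1. Where could a valve result come from?** Tight K holds no valve patients. Brigham is described as a CABG database with valve content unstated. That leaves the NHS cohort, by elimination. The sections on external validation, performance, sub-analysis, analysis populations and sample size (Protocol 7.5, 11.2.1, 11.2.2, 11.3, 11.4; SAP 3.5.1, 3.6, 3.7, 3.8) contain no breakdown by surgery type.

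**2. What can a pooled result hide?** All inputs in this step are assumptions, because the documents give neither the valve share nor AF rates by procedure: 45% valve, AF 25% in CABG and 43% in valve. Pooled AF is 0.55 × 0.25 + 0.45 × 0.43 = 0.331, close to the SAP's 2000/6000 = 0.333. Within-procedure C is set at 0.62 or 0.65, with a normal linear predictor and 1,000,000 simulated patients. The model intercept is set so that pooled O/E is 1.00.

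| Procedure effect carried by the model | Pooled C (within 0.62 / 0.65) | O/E CABG | O/E valve | Pooled slope |
|---|---|---|---|---|
| Full | about 0.66 / 0.68 | 1.00 | 1.00 | about 1.0 |
| Half | about 0.66 / 0.67 | 0.86 | 1.13 | about 1.2 / 1.1 |

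The half-effect O/E can be checked by hand.
- The log-odds are −1.10 at 25% and −0.28 at 43%, a difference of 0.82; half of that is 0.41.
- Keeping the pooled mean at 0.331 gives predicted risks of about 0.291 (CABG) and 0.381 (valve), since 0.55 × 0.291 + 0.45 × 0.381 = 0.331.
- Then 0.25/0.291 = 0.86 and 0.43/0.381 = 1.13.

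The two rows are different models. With the full effect, the pooled C exceeds the within-procedure C, but there is no calibration error by procedure. With half the effect, calibration is wrong in both groups while pooled O/E looks perfect.

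**3. The SAP's own validation sample sizes.**
- O/E: n = (1 − φ)/(φ × SE²) = 0.8/(0.2 × 0.051²) = 1538. This matches.
- Slope: n = I_a/[SE² × (I_a × I_b − I_ab²)], where the I terms are the information on the intercept, the slope and their cross term, with the linear predictor normal with common variance in events and non-events. This gives 4248 at C = 0.725 and 4417 at C = 0.720. The SAP's figure is reproduced if its C of about 0.72 is a rounded value.
- C-statistic: the Newcombe standard error solved for n at C = 0.72 gives 619 with SE = 0.0255 (644 with the printed 0.025).

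**4. Precision in valve patients only.** The inputs are the SAP's 20% prevalence, C = 0.72, and an assumed valve share of 20% to 50%. Slope width scales as 0.2 × √(4417/n); for example, n = 1200 gives 0.2 × √3.68 = 0.38. The full cohort is taken as 12,000: the synopsis total "Prospective: 13, 684" less the 1,684 Tight K patients.

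| Valve share | One year (6000): n | Slope CI width | 12,000: n | Slope CI width |
|---|---|---|---|---|
| 20% | 1200 | 0.38 | 2400 | 0.27 |
| 30% | 1800 | 0.31 | 3600 | 0.22 |
| 40% | 2400 | 0.27 | 4800 | 0.19 |
| 50% | 3000 | 0.24 | 6000 | 0.17 |

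The SAP's slope target is 0.2. Reaching 4248 valve patients needs a share of 4248/6000 = 71% or 4248/12,000 = 35%. At 33% prevalence the one-year widths are 0.33 to 0.21, still above target. O/E width is 0.23 at n = 1200 and at most 0.19 from n = 1800 (target 0.2). C-statistic width is at most 0.072 throughout (target 0.1).

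**The case against.** The strongest reply is that valve surgery is not a stated objective. The sentence on valve surgery sits in a description of data sources, and the aims and eligibility concern cardiac surgery as a whole. For that population, separating higher-risk from lower-risk operations is genuine discrimination, so the pooled result is legitimate. The lay summary names valves and blood vessels together. All of this stands, and it limits the point: the pooled primary outcome is sound as defined. It does not remove the stated need, which appears in both documents without an analysis to meet it.

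The pooled slope also offers some protection. In the half-effect case it is about 1.1 to 1.2, which signals a problem. It does not show which patients are affected.

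Three stronger readings are tempting, and the documents do not support them.
- A reader might infer that pooling always lifts the c-statistic above its value in every procedure. That needs the model to carry the procedure effect and similar within-procedure values. In another assumed case (30% valve), C is 0.70 in non-valve and 0.60 in valve patients, and the pooled C is 0.69. If the model carries no procedure effect, pooled C does not rise (about 0.62 and 0.64), while O/E is about 0.25/0.331 = 0.75 and 0.43/0.331 = 1.30. Nothing in the documents suggests such an omission, since both backgrounds name valve surgery as a risk factor.
- A reader might infer that a valve result cannot be produced. It is only not planned: Protocol 12.3 lists type of cardiac surgery among the likely data.
- A reader might infer that Tight K and the NHS cohort will be compared and need matching on procedure. No such comparison is planned.

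Finally, the NHS cohort's role is inferred by elimination. Protocol 7.5 also mentions the PROPHESY studies, whose case-mix is not given.

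**Conclusion.** The point holds as a gap between a stated purpose and the planned analysis. It should be fixed, but it does not undermine the pooled primary outcome. That no analysis by surgery type is planned follows directly from the documents. The size of possible masking is illustrative only. Under the assumed mix, the pooled C is about 0.03 to 0.04 above the within-procedure value for a model carrying the full procedure effect. For a model carrying half, O/E errors of about 14% (CABG) and 13% (valve) sit behind a pooled O/E of 1.00. These are alternative scenarios and should not be added together.

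A valve analysis on one NHS year would be adequate for discrimination and, from about 1800 valve patients, for O/E. It would miss the SAP's slope target at every assumed share from 20% to 50%. With 12,000 patients the target is met from a share of roughly 35% to 37% (4248 or 4417 out of 12,000).

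**What to change.** Add to SAP 3.8:
- In the NHS data, report the c-statistic, calibration intercept, slope, O/E and calibration plot for PARADISE-1 and PARADISE-2 separately for isolated CABG and for valve surgery with or without CABG. Give 95% confidence intervals and place these beside the pooled result. Use finer procedure groups only if numbers allow.
- Base any statement about performance in valve surgery on these results, not on the pooled figures.
- State the expected number of valve patients and events, and the slope precision they would give.

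The cost is a few extra tables and wider intervals, most noticeably for the slope. Because Protocol 12.3 limits UK extraction to agreed candidate variables and outcomes, confirm that surgery type is among the items extracted.
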